Appendix	
Mapping and Ablation procedure	
Patient questionnaire	

Introduction and purpose of the study

Neuro-mediated cardioinhibitory syncope (SCNM) represents the most frequent form of syncope in the young population without apparent cardiac or neurological pathology (1,2). Although affected young patients have an excellent prognosis, their quality of life can be seriously deteriorated by the frequency of episodes (2,3,4). Definitive cardiac pacing is an effective therapy and is recommended in patients >40 years old (1,2,5,6); there are no trials in patients <40 years old. The general scientific consensus is that in younger patients the role of the pacemaker raises some concerns arising from the need for numerous replacements and possible ventricular remodeling induced by right ventricular pacing over time.

In patients <40 years old with severe recurrent syncope, current practice is to implant loop recorders in order to document the dominant mechanism of syncope, cardioinhibitory or vasodepressor. In cases of asystolic syncope, in the absence of proven effective therapies, recently, transcatheter radiofrequency ablation of the anatomical site areas of the ganglionic plexuses in the right and left atrium has shown promising results, both in the short and long term regarding the treatment of cardioinhibitory reflex syncope (7,8,9,10,11,12,13,14). In Italy, ganglion plexus ablation, so-called cardioneuroablation (CNA) has been current practice in selected cases since 2012 at Policlinico Casilino (15) and the results have been published recently (13). The technique proposed by Caló et al (13), consists of ablation of the ganglionic plexuses of the right atrium. No center currently has sufficient case series to establish long-term efficacy and safety results, for which a multicenter interventional study is therefore needed.

[figure not shown]
In view of these premises, the aim of the study will be to evaluate the efficacy and safety of NAC in patients with SCNM with ECG documentation of spontaneous asystolic episodes of reflex nature.

Study design

ItalianCNA is a multicenter Italian interventional "proof of efficacy" clinical trial that aims to evaluate the incidence of asystolic pauses and heart rate in patients with SCNM who performed CNA after documentation of asystolic pauses on ECG monitoring by implantable loop recorder.

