The study is independent, "investigator-initiated," sponsored by a nonprofit scientific association called the Italian Multidisciplinary Group for the Study of Syncope (GIMSI).

Inclusion criteria

- Age between 18 and 60 years
- Patients with a clinical diagnosis of neuromediated syncope according to class I criteria of the ESC guidelines, Table 1
- Clinical history of recurrent syncope (≥2 in the last year or ≥3 in the last 2 years), severe, not tolerated by the patient
- Documentation of ≥2 asystolic pauses >3 sec daytime on ECG monitoring by implantable loop recorder (ILR), with or without syncope
- Refusal by patient to perform pacemaker implantation

Recommendations	Class	Level
Reflex syncope		
 VVS is highly probable if syncope is precipitated by pain or fear or standing, and is associated with Typical progressive prodrome (pallor, sweating, nausea). 	I	С
 Situational reflex syncope is highly probable if syncope occurs during or immediately after specific triggers. 	I	С

Table 1. Diagnostic criteria of reflex syncope according to ESC guidelines (1,2)

Tilt test is recommended but not mandatory. Patients with negative tilt test are also enrollable. It can be either positive or negative.

Exclusion criteria

- Absence of sinus dysfunction and atrioventricular node disease.
- Absence of structural heart disease
- Possible alternative diagnoses of syncope

Ablative procedure

The ablative procedure involves applying radiofrequency deliveries in the two Right atrium anatomical sites close to the two main ganglionic plexuses of the right atrium:

- **Inferior-posterior area (site of first ablation)** corresponding to the right inferior atrial ganglion located between the inferior vena cava, coronary sinus ostium and near the atrioventricular node
- **Upper-posterior area (site of second ablation)** corresponding to the right superior atrial ganglion located between the superior vena cava and the posterior surface of the right atrium

The method of the ablative procedure is described in detail in the Appendix (see)

Acute success is defined as:

- Shortening of AH interval >20 ms, relative to baseline, persisting for 30 min, and/or Wenckebach point <500 ms at end of procedure plus
- P-P interval <70% of basal P-P interval, or P-P interval <600 ms (calculated as the average of 10 consecutive cycles), after 10 min since the last delivery

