The procedure will be continued until the acute efficacy criteria are met. In case the procedure is terminated without having reached the target, this will be noted as "acute failure"

Follow up (study phase)

It consists of remote monitoring and quarterly questionnaire completed by the patient himself (see appendix).

 Remote monitoring. Central, by an ad hoc established Single Laboratory. All episodes of asystole >3 sec and average monthly heart rate will be recorded

• Patient's self-administered questionnaire. The syncope follow-up questionnaire validated in the BioSync study (6) will be used. Every 3 months the patient will send the questionnaire to the Single Laboratory.

An "Adjudication Committee " consisting of 3 physicians not involved in the study will validate ECG events and questionnaire responses

Endpoint

Main analysis according to intention-to-treat principle. Exploratory subgroup analysis with acute success.

Primary endpoint: Intrapatient comparison of monthly incidence of episodes. asystolic >3 sec before and after CNA

Secondary endpoints:

- Intrapatient comparison of mean heart rate, before and after CNA
- Intrapatient comparison of monthly incidence of (pre)syncopal episodes before and after CNA
- Intrapatient comparison of beat-to-beat variability of heart rate in the short term (spectral analysis) before and after CNA (limited to auxiliary HRV study)

Ancillary substudy (ancillary study): spectral analysis

It consists of acquiring digitized ECG monotrace for 5 minutes the day before and the day after the procedure using surface ECG recording equipment provided free of charge by the promoter. Spectral analysis of the oscillatory components of R-R interval variability will be performed on the ECG trace. This study is optional

Sample calculation

Considering clinically effective a 50% reduction in the monthly incidence of asystole episodes of >3 sec, which before the ablative procedure is assumed to be 0.82 ± 0.67 (16), with 24 patients undergoing ablation, the null hypothesis (Ho: null difference in asystole incidence pre/post-ablation) can be rejected with 80% statistical power at a two-sided t-test with alpha error 0.05.

Bibliography

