Care is taken to avoid ablations in the proximity of the mapped course of the phrenic nerve. To avoid phrenic nerve injury, high amplitude stimulation is performed just before radiofrequency delivery to the superior right atrial GP.

Considering that the exact anatomic borders of GP clusters are unknown, an expanded number of RF applications are delivered in order to form a cloud-like shape ablation surrounding the HAFE tags. An irrigated tip catheter using a contact force >5 g is recommended. P-P interval is carefully monitored. The duration of each single ablation is generally prolonged for at least 30 seconds after stabilization of P-P intervals but does not exceed 60 seconds at the same location. RF applications are interrupted if no significant shortening of the P-P interval is observed within 30 seconds or an ablation index target value of >350-500 or lesion stability index target

value of 4-5.5 is achieved. Points acquired during ablation are annotated by 2 mm tags.

It is recommended that ablation is continued until atrial electrical activity (HAFE) is significantly reduced (peak to peak bipolar electrogram < 0.05 mV) and vagal reflex disappears if present.

It is also recommended, at the end of ablation procedure, to confirm the significant reduction of atrial electrical activity by using of a final voltage map and by showing inability to capture at high output. In addition, a backup stimulation in the right ventricle is performed through a quadripolar catheter in case of prolonged asystolic response evoked during RF.

Basal cycle length, AH and Wenckebach cycle length are reassessed after RF ablation.

After catheter removal, atropine 2 mg (1m + 1m 5 min later) is administrated intravenously > 30 minutes after the last ablation.

Acute procedural **success** is defined as:

 Persistent AH shortening > 20 msec and/or persistent reduction in Wenckebach point cycle length < 500 msec

and

 Post RF P-P interval <70% of the baseline procedural P-P interval or P- P interval >600 msec after 10 minutes of waiting time (as mean value of 10 consecutive cycles)

Post RF inappropriate sinus tachycardia is temporarily treated with beta-blockers or ivabradine.

Patient questionnaire

PATIENT QUESTIONNAIRE

Patient ID:

CNA-----

Date of completion (dd-mm-yyyyy): _____-

QUESTIONNAIRE		
(a) Did you completely lose consciousness for a moment? (syncope, fainting)	☐Yes □ No	

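### Safety is part of the stated aim and post-ablation inappropriate sinus tachycardia is foreseen, but the only follow-up heart-rate analysis is a before/after mean, which cannot show how many patients are affected or for how long

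*Protocol*

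**What the plan says.** - **Aim** (Protocol, Introduction and purpose of the study): "the aim of the study will be to evaluate the efficacy and safety of NAC in patients with SCNM". The same section justifies a multicenter study by the lack of sufficient long-term efficacy and safety results from any one center.
- **Foreseen event** (Appendix, Mapping and Ablation procedure): "Post RF inappropriate sinus tachycardia is temporarily treated with beta-blockers or ivabradine". The protocol gives no definition, count or follow-up of this event.
- **Data collected** (Follow up (study phase)): remote monitoring by a central laboratory and a quarterly patient questionnaire. On the monitoring: "All episodes of asystole >3 sec and average monthly heart rate will be recorded". The questionnaire asks about syncope, presyncope, their circumstances and resulting trauma. It does not ask about palpitations, fast heart rate or drugs.
- **Analysis** (Endpoint): the primary endpoint concerns asystolic pauses. The secondary endpoints are "Intrapatient comparison of mean heart rate, before and after CNA", (pre)syncopal episodes, and short-term heart rate variability in an optional substudy. None is labelled or built as a safety endpoint.
- **Substudy** (Ancillary substudy): "It consists of acquiring digitized ECG monotrace for 5 minutes the day before and the day after the procedure". It cannot inform on heart rate in the months that follow.

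**The concern.** A faster sinus rate is what the procedure is meant to produce acutely, and an excessive, persisting faster rate is the event that the Appendix expects to treat. Both lie on the same variable in the same direction. A before/after comparison of the mean merges them: it carries no count of patients with a large rise and no time course.

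Drug treatment adds a second problem. Patients given a rate-lowering drug contribute lower monthly averages, so the mean, and any count made without regard to drugs, can make the event look absent or resolved.

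At stake is the safety half of the aim. If the protocol is followed as written, the report would contain no statement of how many patients had a sustained high rate, although the monthly averages that would support one are already recorded.

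**Working it through.** **1. Is there a figure of the plan's own to reproduce?** None for heart rate. The number of patients, 24, comes from the Sample calculation, which concerns pauses. With a difference of 0.5 × 0.82 = 0.41 per month, and 0.67 taken as the SD of the within-patient difference, a two-sided paired t-test at 0.05 has 81.9% power with 24 patients. That agrees with the stated 80%. It is used below only as the source of n = 24.

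**2. Is a faster rate an intended effect?** In the main text, one part of acute success is "P-P interval <70% of basal P-P interval, or P-P interval <600 ms". A P-P interval of 600 ms is 60,000/600 = 100 bpm. An interval below 70% of baseline means a rate more than 1/0.70 = 1.43 times baseline. The Appendix gives the second limb the other way round, "P- P interval >600 msec after 10 minutes of waiting time"; the two passages must be reconciled. The reasoning here does not depend on which is meant, because the 70% limb appears in both.

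**3. What can the mean show?** All heart-rate changes below are assumptions for illustration. With *k* of 24 patients changing by *a* and the others by *b*:

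mean = [k·a + (24 − k)·b]/24; SD = |a − b|·√[k(24 − k)/(24·23)]

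| Assumed pattern | Mean change (bpm) | SD of change (bpm) |
|---|---|---|
| 4 at +30, 20 at +5 | (120 + 100)/24 = +9.2 | 25·√(80/552) = 9.5 |
| all 24 at +9.2 | +9.2 | 0 |
| 1 at +20, 23 unchanged | 20/24 = +0.8 | 20·√(23/552) = 4.1 |
| 3 at +40, 21 unchanged | 120/24 = +5.0 | 40·√(63/552) = 13.5 |
| 6 at +40, 18 unchanged | 240/24 = +10.0 | 40·√(108/552) = 17.7 |

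The first two rows share a mean and differ in SD. The SD alone does not identify the affected patients, though. Twelve patients at +18.5 and twelve at −0.15 also have mean +9.2 and SD 18.63·√(144/552) = 9.5, and nobody in that group has a rise of 30.

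**4. Which way can the error run?** In the first row, suppose that a rate-lowering drug brings the four patients back to +5. The mean becomes (24 × 5)/24 = +5.0 with SD 0, and the event has left no trace. Untreated, the same four raise the mean from +5.0 to +9.2. The direction of error is therefore not fixed.

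**5. What would a count show?**
- 4/24 = 16.7%, exact (Clopper-Pearson) 95% CI 4.7% to 37.4%.
- 0/24: upper limit of the two-sided 95% interval = 1 − 0.025^(1/24) = 14.2%. The one-sided 95% bound is 1 − 0.05^(1/24) = 11.7%.
- Probability of at least one case in 24: 1 − 0.95^24 = 71% at an assumed true rate of 5%, and 1 − 0.90^24 = 92% at 10%.

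A count in 24 patients is imprecise, so its interval must be shown with it.

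**The case against.** The strongest reply is that counts, monthly tables and intervals are SAP content, and the SAP is not at hand. That stands for the layout, and it is why one cannot say that the event will go unreported. It does not answer the whole point. The protocol itself fixes the endpoint list and the follow-up sources and declares a safety aim, and nothing in it requires a summary that serves that aim.

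A second reply is that the comparison is within patients, so individual values will exist and a reported SD would reveal unusual spread. This partly stands: the SD of 9.5 bpm in the first illustration would be a warning. It gives neither the number of patients nor the duration.

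Four stronger readings are tempting, and the documents do not support them.

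- *The protocol regards the tachycardia as temporary and leaves that untested.* In the Appendix sentence the adverb qualifies the treatment. No view on how long the tachycardia lasts is stated.
- *Tachycardia will be counted as efficacy and inflate the apparent effect.* Mean heart rate is listed simply as a secondary endpoint, with no direction. The P-P criterion is an acute one, assessed 10 minutes after the last delivery. Treated patients would pull the mean down.
- *The data already collected are enough to detect the event.* A monthly average cannot diagnose inappropriate sinus tachycardia, and without drug records, treated cases would be missed.
- *The protocol calls this event a harm.* It says only that the event is treated.

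**Conclusion.** The point holds in limited form. The protocol has a safety aim, foresees one specific event that needs drugs, lists no safety endpoint, and analyses follow-up heart rate only as a before/after mean. That analysis can show neither the number of patients with an excessive or lasting rise nor its course over time. Under this protocol the event is not planned to be reported; a SAP may supply what is missing.

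The size cannot be taken from the documents, which hold no heart-rate figures. Across the assumed patterns, affected groups of 1 to 6 patients correspond to mean changes from about +0.8 to +10 bpm, values that a uniform modest rise would also give. These patterns assume no drug effect, and treatment can move the mean the other way. The primary endpoint and its sample size are untouched. The change should be made because it decides whether the trial can say anything on this part of its aim.

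**What to change.** Keep the mean heart-rate comparison as it is. Add a descriptive safety summary to the protocol, or to the SAP with a reference from the protocol:

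1. From the monthly averages already recorded, give the number and percentage of patients, with exact 95% CI, above an upper limit that the sponsor's clinicians fix before analysis. Show this for the pre-CNA months, each post-CNA month and last follow-up.
2. Show individual before and after values.
3. Record whether each patient is taking a beta-blocker or ivabradine. Count or flag treated patients separately, so that drug-lowered months are not read as absence or resolution.
4. Describe the count as a screen for sustained high rate, not as a diagnosis of inappropriate sinus tachycardia.

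Separately, reconcile the direction of the 600 ms criterion between the main text and the Appendix.

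Cost: a paragraph of text, one table, agreement on a limit in advance, and one concomitant-drug item to collect. The heart-rate data need no new collection.

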Appendix

Mapping and Ablation procedure

The day before ablation procedure, an ECG is performed in resting conditions and after intravenous administration of atropine. Atropine test is carried out in fasting state with up to 2 mg intravenous atropine sulfate, under continuous ECG recording for 30 minutes (two injections of 1 mg atropine with an interval of 5 minutes). A decrease more than 25% in PP interval is accepted as a positive response.

Mapping and ablation are performed under mild sedation and local anesthesia. Three right femoral vein punctures are performed: a) a decapolar catheter is inserted into the coronary sinus; b) a quadripolar catheter is positioned in the hisian region; c) and a quadripolar deflectable irrigated tip ablation catheter (Navistar SmartTouch, Biosense Webster, Inc or Tacticath, Abbott Inc) is used for mapping and ablation. Electroanatomical mapping of the right atrium (RA) is performed by means of CARTO 3[™] (Biosense Webster, Inc) or by EnSite Precision (Abbott Inc). A three-dimensional anatomical mapping of the RA is performed, during which volume data are recorded continuously during manipulation of the catheter inside the RA. From the outer surface of the volume data acquired, the system generates a surface reconstruction. Tagging the phrenic nerve capture points on the lateral RA allowed us to map the phrenic nerve course. The parameters considered during basal electrophysiological study are: basal cycle length, AH interval and Wenckebach cycle length.

The ablation procedure consists of RF delivering (RF energy at 43°, 30-35 W for 30-60 s) at right atrial anatomic sites where the underlying presence of GP clusters is regarded as highly probable: 1) **the inferior-posterior area** (**first ablation site**): inferior right GP placed between inferior vena cava, coronary sinus ostium and near the atrio-ventricular groove, 2) **the superior-posterior area** (**second ablation site**): superior right atrial GP, adjacent to the junction of the superior vena cava and the posterior surface of RA. The identification of the anatomical target is improved by the

presence of high amplitude fractionated electrograms (HAFE, number of deflections \Box 4, amplitude \Box 0.7 mV and duration \Box 40ms) by using of a single beat analysis in order toquantify number of signal deflections and total activation time and differentiating them by normal electrograms (number of deflections < 4 or duration < 40 ms).

Care is taken to avoid ablations in the proximity of the mapped course of the phrenic nerve. To avoid phrenic nerve injury, high amplitude stimulation is performed just before radiofrequency delivery to the superior right atrial GP.

Considering that the exact anatomic borders of GP clusters are unknown, an expanded number of RF applications are delivered in order to form a cloud-like shape ablation surrounding the HAFE tags. An irrigated tip catheter using a contact force >5 g is recommended. P-P interval is carefully monitored. The duration of each single ablation is generally prolonged for at least 30 seconds after stabilization of P-P intervals but does not exceed 60 seconds at the same location. RF applications are interrupted if no significant shortening of the P-P interval is observed within 30 seconds or an ablation index target value of >350-500 or lesion stability index target

value of 4-5.5 is achieved. Points acquired during ablation are annotated by 2 mm tags.

It is recommended that ablation is continued until atrial electrical activity (HAFE) is significantly reduced (peak to peak bipolar electrogram < 0.05 mV) and vagal reflex disappears if present.

It is also recommended, at the end of ablation procedure, to confirm the significant reduction of atrial electrical activity by using of a final voltage map and by showing inability to capture at high output. In addition, a backup stimulation in the right ventricle is performed through a quadripolar catheter in case of prolonged asystolic response evoked during RF.

Basal cycle length, AH and Wenckebach cycle length are reassessed after RF ablation.

After catheter removal, atropine 2 mg (1m + 1m 5 min later) is administrated intravenously > 30 minutes after the last ablation.

Acute procedural **success** is defined as:

 Persistent AH shortening > 20 msec and/or persistent reduction in Wenckebach point cycle length < 500 msec

and

 Post RF P-P interval <70% of the baseline procedural P-P interval or P- P interval >600 msec after 10 minutes of waiting time (as mean value of 10 consecutive cycles)

Post RF inappropriate sinus tachycardia is temporarily treated with beta-blockers or ivabradine.

Patient questionnaire

PATIENT QUESTIONNAIRE

Patient ID:

CNA-----

Date of completion (dd-mm-yyyyy): _____-

QUESTIONNAIRE		
(a) Did you completely lose consciousness for a moment? (syncope, fainting)	☐Yes □ No	
If yes, do you remember the date it happened? Go to question (c)	dd-mm-yyyyy:	
(b) Or, alternatively, did you recognize any premonitory symptoms of impending loss of consciousness, without being followed by complete loss of consciousness? (presyncope)	☐ Yes No (Note. Answers to (a) and (b) should not both be "Yes.")	
If yes, do you remember the date when it happened?	dd-mm-yyyyy:	
(c) Was the episode characterized by rapid initiation, short duration, and complete spontaneous recovery?	□Yes □ No	
(d) Is the episode similar to those you have had before?	Yes 🗌 No	
(e) Did you have time to stop and lie down/sit down?	Yes 🗌 No	
(f) Did other people witness the episode?	Yes 🗌 No	

	At home
(g) Where did the episode happen?	At work
	On public transportation
	On a private transportation vehicle, while driving.
	On a private transport, but I was not driving
	As I walked down the street Other,
	please specify:
	I was lying
	☐ I was
	□ sitting I
	was
(h) What were you doing immediately before the event?	standing
	I was sitting down from a lying position
	\square I was standing up from a lying position
	I was eating
	\square I was under emotional stress Other,
	please specify:
(i) Did you experience any trauma as a result of the event?	☐ Yes No
(j) Did you go to the emergency room because of the trauma?	Yes No
(k) Were you hospitalized because of the trauma?	Yes No

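### The Appendix reverses the sign of the absolute P-P criterion for acute success: it accepts more than 600 ms where the main text accepts less than 600 ms

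*Protocol*

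**What the plan says.** The Ablative procedure section of the Protocol sets two requirements for acute success, both of which must be met. One concerns AH shortening and/or the Wenckebach point. The other concerns the P-P interval, which must fall below 70% of its basal value or satisfy the absolute alternative, "or P-P interval <600 ms". It is taken as a mean of 10 cycles, 10 minutes after the last delivery.

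The Appendix (Mapping and Ablation procedure) gives its own definition with the same structure. Its P-P requirement reads "Post RF P-P interval <70% of the baseline procedural P-P interval or P- P interval >600 msec after 10 minutes of waiting time", again as a mean of 10 cycles.

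The main text makes acute success an operating rule: "The procedure will be continued until the acute efficacy criteria are met". It adds: "In case the procedure is terminated without having reached the target, this will be noted as" an acute failure. The Endpoint section makes the main analysis intention-to-treat and adds an exploratory analysis of the acute-success subgroup.

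**The concern.** The two definitions share the 70% limit, the 10-cycle mean and the 10-minute wait, but the inequality at 600 ms points in opposite directions. Both are current text, and nothing says which governs. The main text also sends operators to the Appendix for the details of the procedure, where they find a complete success definition with the reversed sign.

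A site working from the Appendix could go wrong in two ways. It could accept a patient whose sinus rate has not responded and stop ablating. It could also reject a partial response that the main text accepts, and then continue ablating or record an acute failure. The P-P interval is the only sinus-rate measure in either definition, since AH and Wenckebach describe AV conduction. In a multicentre trial, sites following different pages would also fill the acute-success subgroup by different rules.

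**Working it through.** **Which sign is wrong.** The rest of the Protocol consistently expects the P-P interval to shorten:

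- The 70% rule, in the same bullet as the disputed limit, rewards shortening.
- The Appendix says of delivery: "RF applications are interrupted if no significant shortening of the P-P interval is observed within 30 seconds".
- For the atropine test the Appendix says: "A decrease more than 25% in PP interval is accepted as a positive response".
- The Appendix provides for treatment of sinus tachycardia after ablation.

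A limit above 600 ms rewards no change, so the Appendix sign is the error.

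**Inputs.** Let B be the baseline P-P and P the post-ablation P-P, both in ms. The limits of 70% and 600 ms come from the two definitions. The AH/Wenckebach requirement is taken as met, and the same B is used for both texts.

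- Main text: pass if P < 0.7B or P < 600, that is, P < max(0.7B, 600).
- Appendix: pass if P < 0.7B or P > 600.

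**Where they differ.** If P < 0.7B, both pass. If P ≥ 0.7B, only the 600 ms limit decides, and the rules disagree at every value except exactly 600 ms, which fails both.

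**Crossover.** 0.7B = 600 gives B = 600/0.7 = 857 ms, a rate of 60,000/857 = 70/min.

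- B above 857 ms: 0.7B exceeds 600, so every P is either below 0.7B or above 600. The Appendix requirement cannot be failed, and the 70% rule does nothing.
- B below 857 ms: the Appendix rejects P from 0.7B to 600 ms. The main text accepts all of that band below 600 ms.
- Any B above 600 ms (rate below 60,000/600 = 100/min): an unchanged rhythm passes the Appendix.

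| Baseline B (ms) | 0.7B (ms) | Band rejected by the Appendix (ms) |
|---|---|---|
| 650 | 455 | 455–600 |
| 700 | 490 | 490–600 |
| 750 | 525 | 525–600 |
| 800 | 560 | 560–600 |
| 900 | 630 | none |

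**Examples (P-P requirement only).**

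| Baseline to post (ms) | Post/baseline | Main text | Appendix |
|---|---|---|---|
| 900 to 850 | 94.4% | fail | pass |
| 700 to 700 | 100% | fail | pass |
| 700 to 560 | 80.0% | pass | fail |
| 800 to 580 | 72.5% | pass | fail |
| 800 to 550 | 68.8% | pass | pass |

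**Sample size.** The planned 24 patients do not depend on acute success. The target difference is 0.5 × 0.82 = 0.41 episodes per month. If the stated SD of 0.67 is taken as the SD of the within-patient difference (an assumption), a two-sided paired t-test at 0.05 has power 0.801 with 23 patients and 0.819 with 24. The stated figure is therefore reproduced closely, and the correction does not touch it.

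**The case against.** The strongest reply is that this is a plain slip that the document itself corrects. The reversed sign stands beside the 70% rule, and an operator who sees that ablation is meant to shorten the P-P interval is unlikely to apply it literally. The main text has the right sign, and the stopping rule and acute-failure label follow directly from it. The main text refers to the Appendix for the method, not for the success definition.

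There are further safeguards. The AH/Wenckebach requirement applies either way. The Appendix also advises: "It is recommended that ablation is continued until atrial electrical activity (HAFE) is significantly reduced", and until any vagal reflex has gone. If the post-ablation intervals are recorded, which is not stated, a wrongly labelled patient could be reclassified later.

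Most of this stands, and it limits the weight of the point. It does not reconcile the two definitions. The additional end-points are recommendations outside the success definition, and a decision to stop ablating cannot be undone afterwards.

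Two smaller points are fair. The main text speaks of a basal interval and the Appendix of a procedural baseline; these are probably the same, but that is an assumption here. The AH/Wenckebach wording differs too: the main text requires AH shortening to last 30 minutes and measures the Wenckebach point at the end of the procedure, while the Appendix asks only for persistence. Correcting the sign alone would not align that wording.

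Some comparison symbols in the Appendix description of fractionated electrograms are unreadable in the text at hand. Those in the success definition are legible, so a misread sign is unlikely, though not excluded.

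**Conclusion.** The concern holds. Two current definitions of acute success contradict each other at the 600 ms limit, and the Appendix is wrong. It errs in both directions: above a baseline of 857 ms its P-P requirement is empty, and below that it rejects responses between 70% of baseline and 600 ms that the main text accepts, apart from exactly 600 ms.

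The consequences are confined to the stopping decision, the acute-failure label and the exploratory subgroup. The calculation assumes that the AH/Wenckebach requirement is met and that both texts mean the same baseline. It describes where the rules differ, not how many patients fall there. The point should be fixed, but it does not threaten the main analysis.

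**What to change.** In the Appendix, change the absolute P-P alternative to less than 600 ms. Add a sentence stating that the acute-success definition in the Ablative procedure section governs; this also settles the differences in the AH/Wenckebach wording. Send sites a short notice of the correction.

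The cost is one sign, one cross-reference and one notice. No new measurement is needed, and neither the sample size nor the main analysis changes.

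### The quarterly symptom form gives no recall period, so an undated or misdated episode cannot be reliably placed after CNA or recognised as already reported (secondary endpoint only)

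*Protocol*

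**What the plan says.** The Protocol's Follow up (study phase) section has two components: remote monitoring, which records asystolic episodes and monthly mean heart rate, and a patient-completed form. On the form it says: "Every 3 months the patient will send the questionnaire to the Single Laboratory". No other source of post-CNA symptoms is named. Under Endpoint, a secondary comparison uses the monthly incidence of syncope and presyncope in each patient before and after CNA.

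The form is printed in the Appendix under Patient questionnaire. The syncope item is "a) Did you completely lose consciousness for a moment? (syncope, fainting", followed by "If yes, do you remember the date it happened? Go to question (c". The presyncope item is "b) Or, alternatively, did you recognize any premonitory symptoms of impending loss of consciousness, without being followed by complete loss of consciousness? (presyncope", followed by "If yes, do you remember the date when it happened". Neither item names a period, and no heading or instruction on the form supplies one. The form does carry a patient ID and a completion date ("Date of completion (dd-mm-yyyyy").

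The Inclusion criteria require "Clinical history of recurrent syncope (≥2 in the last year or ≥3 in the last 2 years" episodes. The Follow up section also sets up an adjudication committee "consisting of 3 physicians not involved in the study will validate ECG events and questionnaire responses".

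**The concern.** A monthly incidence needs each episode to fall in a known window. Read literally, the syncope item asks whether the patient has ever lost consciousness, and under the inclusion criteria every patient has. A patient with no event since CNA could truthfully answer Yes on the first form. A patient with one post-CNA syncope could truthfully answer Yes on every later form.

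The episode date would settle the matter, but it is asked as a question about memory and can be left blank. A blank or wrong date leaves little to show on which side of the ablation the episode lies, or whether it has been reported before. The loop recorder does not always fill the gap: monitoring logs pauses over 3 seconds, and a syncope or presyncope without such a pause leaves no recorded pause to date it by.

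At stake is the accuracy of the post-CNA symptom rate in a single-arm before/after comparison. Analysis cannot later restore a period that patients were never asked about.

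**Working it through.** **1. Does any planned figure depend on the form?** The only calculated figure is the sample size, which is for asystolic episodes. Inputs from Sample calculation: pre-ablation rate 0.82 per month, SD 0.67, 50% reduction, two-sided alpha 0.05, 80% power, 24 patients.

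- Difference = 0.5 × 0.82 = 0.41 per month.
- Paired t-test, taking 0.67 as the SD of the within-patient difference (an assumption; the protocol does not say which SD it is): 23 patients give 80.1% power and 24 give 81.9%.
- Normal approximation: ((1.96 + 0.84) × 0.67 / 0.41)² ≈ 21.

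On that assumption the stated 24 is reproduced closely. No input comes from the questionnaire, so the point below does not change it.

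**2. Which answers are at risk?**

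| Answer on the form | Can it be placed? |
|---|---|
| Yes, correct date before CNA | Yes: recognisable as pre-CNA |
| Yes, correct date matching an earlier form | Yes: recognisable as a repeat |
| Yes, correct new date after CNA | Yes: counted once |
| Yes, no date | Not reliably: the completion date shows when the form was filled in, not when the episode happened |
| Yes, wrong date | Not reliably |

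Only the last two rows are a problem. The documents give no figure for how often they will occur.

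**3. Effect of repeats on the endpoint (assumption, not data).** Suppose the true post/pre ratio of (pre)syncope rates is 0.50 and a fraction q of post-CNA episodes is counted twice. The observed ratio is 0.50 × (1 + q):

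| q | Observed ratio |
|---|---|
| 5% | 0.525 |
| 10% | 0.55 |
| 20% | 0.60 |
| 30% | 0.65 |

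**4. Extreme case for one patient.** One syncope in the first quarter, reported again on all four forms of a year, never dated and accepted as new each time, gives 4/12 = 0.33 per month instead of 1/12 = 0.083. The arithmetic is right, but all of these conditions must hold together.

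**5. The opposite error.** As printed, the form has one date field for each of items (a) and (b), and it says that both should not be answered Yes. If one form therefore records one episode, the most it can show is 1 per 3 months = 0.33 per month. A patient with two episodes in a quarter (2/3 = 0.67 per month) would be recorded at half the true rate. That error lowers the post-CNA count.

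**The case against.** The strongest defence is that the form is sensible in context. It is sent during follow-up, at fixed 3-month intervals, to patients who know that they have had an ablation. Item (d) asks whether the episode resembles previous ones, which treats it as new. Most patients will probably answer for the time since the last form. Items (c) and (e) to (k) describe onset and recovery, chance to sit or lie down, witnesses, place, activity, trauma and its consequences. With the patient ID, this lets the committee compare an undated episode with those on earlier forms. Rules for undated or duplicate events may also sit in an SAP or adjudication charter that is not shown, and the protocol describes the form as validated in a previous trial.

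Much of this stands. It disposes of the broader reading that a reader might infer, that any old episode can simply be reported again and counted as post-CNA: a correctly dated one can be recognised and excluded. The descriptive items weaken, too, any claim that the committee is helpless when the date is blank, although a similar profile does not prove a repeat, since recurrent reflex syncope may well look alike from one episode to the next. The absence of a handling rule is not itself the point.

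What does not fall away is the wording. The protocol fixes the text of the form, that text has no period, and a later rule can only assume which period the patient had in mind. The reference to validation does not supply a period on the form printed here.

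**Conclusion.** The point holds in a limited form. Items (a) and (b) name no recall period on a form repeated every 3 months, so an undated or misdated Yes cannot be reliably placed after CNA or recognised as already reported. Dated episodes can be sorted by the committee. Only the secondary (pre)syncope endpoint is affected. The primary endpoint comes from central loop-recorder monitoring and is untouched.

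The size is unknown, because the share of undated or repeated answers is not in the documents. The range of 0.525 to 0.65 rests on an assumed true ratio of 0.50 and assumed double-counting of 5% to 30%.

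Two further inferences are tempting and are not supported. One is that the symptom endpoint is biased against CNA: repeats would act that way, but the limited room for several episodes in a quarter acts the other way, and the net direction is not established. The other is a fourfold inflation of the rate, which is a worst case for one patient and not an expected effect. Severity is minor; this is a worthwhile improvement to the instrument.

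**What to change.** Add the period to items (a) and (b): *since you sent your last questionnaire (first form: since the ablation)*, with the start date of that period pre-printed on each form. Assign an undated Yes to the period printed on the form on which it appears.

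The cost is one line on the form before the next mailing, plus filling in the start date for each patient. The drawback is a small departure from the wording of the validated form. The change cannot rescue undated answers on forms already returned, and it reduces but does not remove errors in remembered dates.

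It does not address several episodes in one quarter.
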